- Evaluate the relationships between KZR-616 PK, clinical efficacy, clinical safety, and various PD endpoints related to skin and muscle biopsy histology and gene expression profiles.

INVESTIGATIONAL PRODUCT(S), DOSE AND MODE OF ADMINISTRATION

Active Product	Dosage form: KZR-616 Lyophile, 125 mg/vial, is supplied as a refrigerated lyophilized drug product containing 125 mg of KZR-616 (150 mg of KZR-616 maleate) and [REDACTED] (inactive excipient) in single-use 3.0-mL borosilicate glass vial. Dose and dose frequency:
-----------------------	---

	
The study consists of 2 arms:
 
Arm A:
 
 • Treatment Period 1: KZR-616 30 mg SC weekly for 2 weeks (W0-W1), then 45 mg SC weekly for 14 weeks (W2-W15) • Treatment Period 2: Placebo SC weekly for 16 weeks (W16-W31). 
Arm B:
 
 • Treatment Period 1: Placebo SC weekly for 16 weeks (W0-W15) • Treatment Period 2: KZR-616 30 mg SC weekly for 2 weeks (W16-W17), then 45 mg SC weekly for 14 weeks (W18-W31).
Control/Comparator	
A placebo control will be used to maintain blinding and will be sterile water for injection (WFI).
 
Dose and dose frequency: Refer to the dose and dose frequency of the active product, KZR-616.

PATIENT SELECTION	
Targeted Accrual	Approximately 24 enrolled patients; it is anticipated 40 patients will be screened to achieve 24 patients enrolled
Number of Arms	Two with approximately 12 patients in each arm
Planned Number of Sites	Up to approximately 18 sites

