2.2. Study Endpoints

2.2.1. Efficacy Endpoints

The primary efficacy endpoint is:

- Mean change from start to end of KZR-616 treatment in the Total Improvement Score (TIS), which ranges from 0 to 100.

Secondary efficacy endpoints are:

- Proportion of patients with an increase ≥ 20 points on the TIS from start to end of KZR-616 treatment. The categories and ranges of scores for improvement are: 20-39 points being minimal improvement, 40-59 points being moderate improvement, and ≥ 60 points being major improvement
- Proportion of patients from start to end of KZR-616 treatment meeting International Myositis Assessment and Clinical Studies Group (IMACS) Definition of Improvement (DOI). The IMACS DOI is $\geq 20\%$ improvement in at least 3 of 6 core set activity measures, with no more than 2 core set activity measures (CSAMs) worsening by $\geq 25\%$ (the Manual Muscle Testing-8 Muscle Groups [MMT-8] cannot be a worsening measure)
- Absolute change and percent change from start to end of KZR-616 treatment in the IMACS individual CSAMs
- For patients with DM, the mean change from start to end of KZR-616 treatment in the Cutaneous Dermatomyositis Disease Area and Severity Index (CDASI)
- For patients with DM, the mean change from start to end of KZR-616 treatment in the Peak Pruritus Numeric Rating Scale (NRS).

Exploratory efficacy endpoints are:

- Mean change over time from start to end of KZR-616 treatment in the TIS in all patients, patients with DM only, and in patients with PM only
- Proportion of patients over time with an increase of ≥ 20 , ≥ 40 , or ≥ 60 points on the TIS from start to end of KZR-616 treatment in all patients, in patients with DM only, and in patients with PM only
- For patients with an increase of ≥ 20 points on the TIS from Baseline to W16, the proportion of patients with no change or increase in their TIS at W32 for all patients, in patients with DM only, and in patients with PM only
- Mean change and mean percent change over time from start to end of KZR-616 treatment in the IMACS individual CSAMs and core set damage measures (CSDMs) for all patients, in patients with DM only, and in patients with PM only
- Mean change from Baseline over time from start to end of KZR-616 treatment in the FI-2, the FI-3 and the individual components of the FI-3 for all patients, in patients with DM only, and in patients with PM only
- For patients with DM, mean change over time from start to end of KZR-616 treatment in the CDASI

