3. STUDY DESIGN

3.1. Type and Design of Study

This is a Phase 2 randomized, double-blind, placebo-controlled, crossover, multicenter study designed to evaluate the safety, tolerability, efficacy, PK, and PD of treatment with KZR-616 in patients with active PM or DM.

Patients will be evaluated for eligibility during the Screening Period. Eligible patients will be allocated in a 1:1 fashion to a randomized treatment arm (Arm A or Arm B). Patients will be stratified by their diagnosis of PM or DM.

During the 32-week treatment period, patients will receive study drug SC once weekly. The 16 weeks of dosing during Treatment Period 1 begins at Week (W) 0 and continues through W15 (ie, ends immediately before dosing at Week 16 [approximately Day 113]); patients allocated to Arm A will receive KZR-616 and those in Arm B will receive placebo. The 16 weeks of dosing during Treatment Period 2 begins with administration of the first dose at W16 and continues through W31 (ie, ends immediately before Week 32); patients allocated to Arm A will receive placebo and those in Arm B will receive KZR-616.

This study will be conducted on an outpatient basis. Study visits will occur at Screening, W0, W4, W8, W12, W16, W20, W24, W28, W32, W36, and W40. Day 1 of W0 will be defined as Baseline. The W36 and W40 visits will comprise the Safety Follow-up (SFU).

Randomized patients who withdraw from the study prior to W32 will be requested to undergo the Early Termination Visit (ETV) procedures, and all patients who withdraw prematurely also will be requested to return for a SFU visit 9 weeks (W40 visit procedures) after receipt of their last dose of the study drug.

Efficacy assessments will be performed for all patients, unless indicated otherwise, and will include:

- IMACS core set Activity and Damage measures
 - MMT-8
 - Physician Global Assessment (MDGA)
 - Patient Global Assessments of Disease Activity (PtGADA)
 - Health Assessment Questionnaire-Disability Index (HAQ-DI)
 - Muscle enzymes (clinical laboratory assessments): CK, aldolase, LDH, alanine aminotransferase (ALT), and aspartate aminotransferase (AST)
 - Myositis Disease Activity Assessment Tool (MDAAT, 2005 version)
 - Myositis Damage Index (MDI)
 - Patient Global Assessment of Disease Damage (PtGADD).
- Functional Index-2 (FI-2, performed for the dominant side only).
- Functional Index-3 (FI-3) assessments:
 - 30-second chair stand test

- Timed up and go test
- 6-minute walk distance.
- MDGIC

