3.1.3. Study Design Rationale

This placebo-controlled double-blind crossover study is designed to minimize bias in the evaluation of KZR-616 in patients with DM/PM and to maximize the opportunity for each patient to contribute data. All patients may still receive background treatment in the form of the allowed concomitant therapies as described in the study exclusion criteria ([Section 4.3](#)). A crossover design was selected for use in this study to:

- Increase the power of the study because not only will there be the opportunity for evaluation of between-group comparisons, but the patients initially treated with placebo can serve as their own controls
- Data for bortezomib allude to maintenance of effect of proteasome inhibition postdosing.³ The Treatment and SFU Periods allow for evaluation of the treated population after drug discontinuation in terms of both safety and efficacy; these data are best obtained from those patients that start on KZR-616 first and then cross over to placebo.

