3.2. Minimization of Bias

3.2.1. Randomization

Patients will be allocated to a randomized treatment sequence (Arm A: KZR-616 followed by placebo; Arm B: placebo followed by KZR-616) in a 1:1 fashion. Patients will receive the first assigned study drug treatment in Treatment Period 1 (W0 through before dosing at W16)

and cross over to receive the next study drug treatment beginning on the first day of Treatment Period 2 (administration of the first dose at W16 through W32). Patients will be stratified according to their diagnosis of PM or DM. Patients will be stratified by their diagnosis of DM or PM.

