10.1. Sample Size Calculation

Prior summary statistics on change from Baseline in TIS score are not available. Hence, statistical power is quantified via standardized effect size (mean difference divided by pooled standard deviation [SD]). A sample size of 24 patients has 80% power to yield a statistically significant ($\alpha=0.05$ 2-sided) improvement from Baseline if the true underlying effect size is 0.6 (90% power if true effect size is 0.7). The minimum observed effect size that would yield statistical significance is 0.42. This level of statistical precision is thought to be adequate for this initial trial of KZR-616 in PM and DM.

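### The exploratory endpoint on Week 16 TIS responders at Week 32 has no arm restriction, so it pools drug responders followed on placebo with placebo responders followed on drug

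*Combined protocol and SAP*

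**What the plan says.** The endpoint is in the exploratory list of Section 2.2.1 and is repeated in the synopsis. Its entry condition is "For patients with an increase of ≥ 20 points on the TIS from Baseline to W16". Its outcome is "the proportion of patients with no change or increase in their TIS at W32 for all patients", followed by the same proportion in DM only and in PM only. No arm or treatment is named.

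Section 3.2.1 sets out the sequences: "Patients will be allocated to a randomized treatment sequence (Arm A: KZR-616 followed by placebo; Arm B: placebo followed by KZR-616) in a 1:1 fashion". For Treatment Period 2, which fills the interval between the endpoint's two time points, Section 3.1 states that "patients allocated to Arm A will receive placebo and those in Arm B will receive KZR-616". Table 1 in Section 6.1 agrees.

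Section 3.1.3 gives the reasons for the crossover. One is that "Data for bortezomib allude to maintenance of effect of proteasome inhibition postdosing". The section adds that the design allows patients to be evaluated after the drug is stopped, for safety and efficacy, and that "these data are best obtained from those patients that start on KZR-616 first and then cross over to placebo".

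Section 10.3 summarises binary endpoints by counts, percentages and Clopper-Pearson intervals, and leaves further analyses to the SAP. Section 10.2 bases all summaries on the treatment actually received.

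**The concern.** Every other efficacy endpoint in Section 2.2.1 is anchored to the start and end of KZR-616 treatment, which lines the two arms up by exposure. This one alone uses fixed study weeks. In a crossover, fixed weeks mean opposite things in the two arms: Week 16 to Week 32 is withdrawal in Arm A and first exposure in Arm B.

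It is also the only listed efficacy endpoint that follows Week 16 responders to Week 32. It is therefore the natural place to look for persistence of effect after KZR-616 is stopped, which Section 3.1.3 gives as a reason for the design. Persistence in Arm A also bears on carryover, which Section 10.3 treats as unknown when it makes the crossover analysis exploratory. A pooled percentage blurs that information and could be quoted as maintenance of effect when part of it was observed on active drug.

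**Working it through.** **Figures in the plan.** The protocol states no figure for this endpoint. The figures in Section 10.1 concern the primary within-patient analysis. A paired t-test with 24 patients (23 df, noncentrality d√24, two-sided 0.05) gives power of 80.4% at d = 0.6 and 90.7% at d = 0.7. The smallest significant observed effect is t(0.975, 23)/√24 = 0.422. All three agree with the stated 80%, 90% and 0.42, and nothing below changes them.

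**Who is in the denominator** (Sections 2.2.1, 3.1 and 3.2.1)

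| | Weeks 0–16 | Weeks 16–32 | What no loss of TIS at Week 32 describes |
|---|---|---|---|
| Arm A, TIS ≥ 20 at Week 16 | KZR-616 | placebo | persistence after stopping KZR-616 |
| Arm B, TIS ≥ 20 at Week 16 | placebo | KZR-616 | a placebo-period response held or increased on KZR-616 |

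The comparison at Week 32 is read here as against Week 16.

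**Formula.** Let nA and nB be the Week 16 responders in each arm, mA and mB the proportions holding their TIS at Week 32, and s = nB/(nA + nB). Then

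pooled = (nA·mA + nB·mB)/(nA + nB) = mA + s·(mB − mA).

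The pooled figure differs from the Arm A figure by s × (mB − mA). Both size and sign depend on the gap between arms.

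**Inputs.** The synopsis gives the arm size: "Two with approximately 12 patients in each arm". The documents give no Week 16 response rates and no Week 32 rates, so all of these are assumptions.

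| Assumed Week 16 response, A / B | nA | nB | s |
|---|---|---|---|
| 60% / 20% | 7.2 | 2.4 | 25% |
| 60% / 40% | 7.2 | 4.8 | 40% |
| 70% / 50% | 8.4 | 6.0 | 42% |
| 50% / 50% | 6.0 | 6.0 | 50% |

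**Shift from the Arm A figure, s × gap**

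| Gap mB − mA | s = 25% | s = 50% |
|---|---|---|
| 0 points | 0 | 0 |
| 10 points | 2.5 | 5 |
| 40 points | 10 | 20 |
| 50 points | 12.5 | 25 |
| −10 points | −2.5 | −5 |

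One case in full: response 60% / 40%, with mA = 50% and mB = 90%, gives 0.50 + 0.40 × 0.40 = 0.66. The report would show 66% where the off-drug figure is 50%. With mA = mB = 50% it would show 50%, which is numerically unchanged but still a mixture.

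**Precision if restricted to Arm A.** With 12 patients and a response of 50–70%, the denominator is 12 × 0.5 = 6 to 12 × 0.7 = 8.4, so about 6–8. The Clopper-Pearson 95% interval for 3/6 is 12–88%. At the ceiling of 12 responders, 6/12 gives 21–79%.

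**The case against.** The protocol never labels this endpoint as durability or maintenance. Taken literally it describes Week 32 status among Week 16 responders. Section 3.1.3 does not mention it, and only says where post-discontinuation data are best sought. The phrase about all patients belongs to a formula used throughout the exploratory list (all, DM only, PM only) and may not be an instruction to pool arms. Where the primary analysis combines the sequences, Section 2.2.1 says so, and this item does not. Section 10.2 ties summaries to the treatment received, and Section 10 promises a detailed SAP that could present the endpoint by arm. The endpoint is exploratory and descriptive, and the Arm A subset can be tabulated from data already collected.

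Much of this stands, and it limits the point. Three stronger inferences are not supported:

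- A reader might infer that the figure must be biased towards good persistence. That needs Arm B to hold its TIS better than Arm A. The documents give no rates. Arm B patients selected for a high score on placebo may regress, and Arm A may carry over.
- A reader might take 10–25 points as the typical distortion. That range comes only from assumed gaps of 40–50 points.
- A reader might infer that Section 3.1.3 confines persistence data to Arm A. It states a preference.

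The objection does not supply a rule that separates the arms. Even if the phrase only contrasts with DM and PM, nothing excludes Arm B. The treatment-received rule does not classify an endpoint that starts on one treatment and ends on the other. An unspecified later analysis is not a commitment to split this one.

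**Conclusion.** The point holds as a defect of definition. Followed as written, the endpoint pools two groups with opposite treatment histories, and its value answers neither the persistence question nor the treatment-response question. This follows from the endpoint wording and the treatment sequences and needs no assumed rates.

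The numerical effect is conditional. It is zero if the arms hold their TIS equally, 2.5–5 points for a 10-point gap and about 10–25 points for a 40- to 50-point gap, with Arm B at an assumed 25–50% of the denominator. It overstates off-drug persistence only when Arm B does better on KZR-616 than Arm A does on placebo, and it reverses if the gap is negative.

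Severity is low. The endpoint is exploratory and descriptive, and the primary result, the type 1 error level and the sample size are unaffected.

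**What to change.** In Section 2.2.1 and the synopsis, define the endpoint by randomised sequence:

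- For persistence after KZR-616, use Arm A patients with a TIS of at least 20 at Week 16 and report the proportion whose TIS at Week 32 is no lower than at Week 16.
- Report the Week 32 status of Arm B patients who reached 20 points on placebo on a separate line, and do not call it maintenance.

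Carry the same split into the SAP tables. It needs no new assessments, since both arms are seen at both visits.

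The cost is precision. The Arm A denominator is at most about 12 and more likely about 6–8 under assumed response rates of 50–70%, so the interval will be wide (for example 12–88% for 3/6). The DM and PM splits within Arm A will be smaller still and are best shown as counts.

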2.2.2. Safety Endpoints

Safety endpoints are:

- Incidence, nature, and severity of AEs
- Incidence, nature, and severity of SAEs
- Incidence and severity of infection-related AEs and SAEs
- Incidence and severity of AEs with onset within 24 hours from the start of dosing with any study drug
- Incidence of AEs leading to study drug discontinuation
- Changes in standard laboratory parameters, vital signs, and ECGs.

2.2.3. Pharmacokinetic and Pharmacodynamic Endpoints

The secondary PK endpoint will:

- Evaluate the plasma PK parameters for KZR-616 and its metabolite KZR-59587.

The exploratory PK/PD endpoints will:

- Evaluate the relationships between KZR-616 PK, clinical efficacy, clinical safety, and various PD endpoints including proteasome inhibition and changes in circulating cytokine and immune cell profiles
- Evaluate the relationships between KZR-616 PK, clinical efficacy, clinical safety, and various PD endpoints related to skin and muscle biopsy histology and gene expression profiles.

3. STUDY DESIGN

3.1. Type and Design of Study

This is a Phase 2 randomized, double-blind, placebo-controlled, crossover, multicenter study designed to evaluate the safety, tolerability, efficacy, PK, and PD of treatment with KZR-616 in patients with active PM or DM.

Patients will be evaluated for eligibility during the Screening Period. Eligible patients will be allocated in a 1:1 fashion to a randomized treatment arm (Arm A or Arm B). Patients will be stratified by their diagnosis of PM or DM.

During the 32-week treatment period, patients will receive study drug SC once weekly. The 16 weeks of dosing during Treatment Period 1 begins at Week (W) 0 and continues through W15 (ie, ends immediately before dosing at Week 16 [approximately Day 113]); patients allocated to Arm A will receive KZR-616 and those in Arm B will receive placebo. The 16 weeks of dosing during Treatment Period 2 begins with administration of the first dose at W16 and continues through W31 (ie, ends immediately before Week 32); patients allocated to Arm A will receive placebo and those in Arm B will receive KZR-616.

This study will be conducted on an outpatient basis. Study visits will occur at Screening, W0, W4, W8, W12, W16, W20, W24, W28, W32, W36, and W40. Day 1 of W0 will be defined as Baseline. The W36 and W40 visits will comprise the Safety Follow-up (SFU).

Randomized patients who withdraw from the study prior to W32 will be requested to undergo the Early Termination Visit (ETV) procedures, and all patients who withdraw prematurely also will be requested to return for a SFU visit 9 weeks (W40 visit procedures) after receipt of their last dose of the study drug.

Efficacy assessments will be performed for all patients, unless indicated otherwise, and will include:

- IMACS core set Activity and Damage measures
 - MMT-8
 - Physician Global Assessment (MDGA)
 - Patient Global Assessments of Disease Activity (PtGADA)
 - Health Assessment Questionnaire-Disability Index (HAQ-DI)
 - Muscle enzymes (clinical laboratory assessments): CK, aldolase, LDH, alanine aminotransferase (ALT), and aspartate aminotransferase (AST)
 - Myositis Disease Activity Assessment Tool (MDAAT, 2005 version)
 - Myositis Damage Index (MDI)
 - Patient Global Assessment of Disease Damage (PtGADD).
- Functional Index-2 (FI-2, performed for the dominant side only).
- Functional Index-3 (FI-3) assessments:
 - 30-second chair stand test

- Timed up and go test
- 6-minute walk distance.
- MDGIC
- CDASI, performed only for patients with DM.

Additional patient reported outcome measures (PROMs) will be performed by all patients, unless indicated otherwise, and will include:

[figure not shown]
- PROMIS-29
- EQ-5D-5L
- HRU
- TSQM
- PGIC
- Peak Pruritus NRS, performed only by patients with DM.

Safety will be assessed throughout the study by monitoring of vital signs (blood pressure, pulse rate, temperature, and respiration rate), laboratory tests (hematology, chemistry, urinalysis, immunoglobulins), ECGs, and physical exams; and by recording and analyzing all AEs and SAEs.

Biopsies will be collected from a subset of enrolled patients; skin biopsies will be performed only for selected patients with DM, and muscle biopsies will be performed for selected patients with PM or DM. For selected patients, biopsies will be collected from skin and/or muscle at Baseline, W16, and optionally at W32. The tissue samples will be used for exploratory investigations of treatment-related changes and regulation of inflammatory pathways. Complete instructions for the collection and processing of biopsy samples will be included in the Laboratory Manual.

The study design schema is presented in [Figure 1](#).

Figure 1 **Study Design Schema**

a Treatment Period 1 is from Day 1 of Week 0 and continues until immediately before dosing at Week 16 (approximately Day 113). Treatment Period 2 begins with administration of the first dose at Week 16 and continues through Week 32.

b In Treatment Periods 1 and 2, KZR-616 30 mg will be administered for the first 2 doses of each treatment period followed by administration of KZR-616 45 mg for the remaining 14 doses of each Treatment Period.

3.1.1. Sequence and Duration of Study Periods

The study comprises a 4-week Screening Period, a 32-week Treatment Period divided into two 16-week periods, and an 8-week SFU.

Individual patients will participate for approximately 44 weeks, inclusive of the Screening and SFU Periods.

3.1.2. Dose and Regimen Rationale

The planned doses of KZR-616 for administration in this study are 30 and 45 mg SC once weekly for 16 consecutive weeks; 30 mg doses will be administered the first 2 weeks (ie, the first 2 doses of the Treatment Period) followed by administration of 45 mg doses for the remaining 14 weeks of the Treatment Period.

In a Phase 1 study in healthy volunteers and a Phase 1b study in SLE patients, weekly SC administration of 45 mg was determined to be tolerated and resulted in potent and selective inhibition of the immunoproteasome. Anticipated levels of exposure with KZR-616 45 mg SC once weekly are lower than those achieved at the NOAEL for rats and monkeys. The profile of immunoproteasome inhibition at this dose correlated with anti-inflammatory activity in nonclinical models at the minimally efficacious dose.

The duration of dosing per treatment period will be 16 weeks. This is to allow adequate time to detect a change in muscle strength while minimizing the time patients spend on placebo.

3.1.3. Study Design Rationale

This placebo-controlled double-blind crossover study is designed to minimize bias in the evaluation of KZR-616 in patients with DM/PM and to maximize the opportunity for each patient to contribute data. All patients may still receive background treatment in the form of the allowed concomitant therapies as described in the study exclusion criteria ([Section 4.3](#)). A crossover design was selected for use in this study to:

- Increase the power of the study because not only will there be the opportunity for evaluation of between-group comparisons, but the patients initially treated with placebo can serve as their own controls
- Data for bortezomib allude to maintenance of effect of proteasome inhibition postdosing.³ The Treatment and SFU Periods allow for evaluation of the treated population after drug discontinuation in terms of both safety and efficacy; these data are best obtained from those patients that start on KZR-616 first and then cross over to placebo.

